4.4.2.3 Baseline FV (dengue, YF, and Zika) Status

Baseline FV status is defined as the presence of neutralizing Abs against YF virus and/or Zika virus and/or positive Anti-NS1 ELISA result in the blood sample collected at V01 before vaccination in the present study from all subjects.

- **Immune:** subjects with quantified (\geq LLOQ) neutralizing Abs against YF virus, and/or Zika virus (≥ 100), and/or positive Anti-NS1 ELISA result.
- **Non-immune:** subjects without quantified (< LLOQ) neutralizing Abs against YF and without Ab against Zika (< 100) and negative Anti-NS1 ELISA result. To be classified in this

category, the titer results at baseline must be available and valid, ie, not coded ‘NR’ in the serology database.

- **Missing:** subjects with all the titer values missing.
- **Undetermined:** subjects do not meet the criteria for at least one of the above three categories, eg, a subject with a value < LLOQ against YF virus and/or Zika virus (<100) and/or negative Anti-NS1 ELISA result and non-valid titer results (ie, ‘Missing’ or coded ‘NR’ in the serology database).

Similarly, the following baseline statuses with 3 identical categories (ie, Immune, Non-immune and Missing) are defined for:

- Baseline dengue status: considering Anti-NS1 IgG
- Baseline YF status: considering neutralizing Abs against YF
- Baseline Zika status: considering neutralizing Abs against Zika

The LLOQ for YF and Zika and dengue neutralizing Abs is 10 (1/dil). Positive Anti-NS1 is defined as ≥ 9 ELISA unit/mL.

4.4.3 Efficacy

Not applicable.

4.4.4 Derived Other Variables

4.4.4.1 Age for Demographics

The age of a subject is the age computed automatically in the eCRF, and presented as an integer.⁵

4.4.4.2 Duration of a Subject in the Trial

The duration of a subject in the study is computed as follows: Maximum (date of visit, date of term form, follow-up date, date of last contact) – date of V01 +1.

4.4.4.3 Duration of the Study

The duration of the study is computed in days as follows: Latest date of all subjects (termination date, last visit date, date of last contact) – earliest date of all subjects (date of visit V01) +1.

5 Statistical Methods and Determination of Sample Size

The statistical analyses will be performed under the responsibility of the Sponsor’s Biostatistics platform using SAS® Version 9.4 software or later. The final analysis will be conducted once the 6-month safety data have been collected and the final database lock has occurred. No statistical adjustment is necessary because no hypotheses will be tested.

For descriptive purposes, the following statistics will be presented:

Table 5.1: Descriptive statistics produced

Baseline characteristics and follow-up description	Categorical data	Number of subjects. Percentage of subjects.
	Continuous data	Mean, standard deviation, quartiles, minimum, and maximum.
Clinical safety results	Categorical data (AEs)	Solicited: Number and percentage (95% CIs) of subjects. Unsolicited: Number and percentage (95% CIs) of subjects, and number of events.
	Categorical data (decrease in CD4 count, increase in HIV viral load, virologically-confirmed dengue case)	Number of subjects Percentage of subjects
Viremia	Categorical data	Number and percentage of subjects with a detectable or quantified viremia (possibly 95% CI of the percentage of the subjects)
	Continuous data	Mean, standard deviation, minimum and maximum (possibly median and quartiles) on quantified viremia data.
Immunogenicity results	Categorical data (cutoff)	Number and percentage (95% CIs) of subjects.
	Continuous data (titer/data)	Log10: Mean and standard deviation. Anti-Log10 (work on Log10 distribution, and anti-Log10 applied): Geometric mean, 95% CI of the geometric mean, quartiles, minimum, and maximum. Graphical representation by Reverse Cumulative Distribution Curve (RCDC).

The confidence interval (CI) for the single proportion will be calculated using the exact binomial method (Clopper-Pearson method, quoted by Newcombe (21), ie, using the inverse of the beta integral with SAS).

For immunogenicity results, assuming that Log10 transformation of the titers / data follows a normal distribution, at first, the mean and the 95% CI will be calculated on Log10 (titers/data) using the usual calculation for normal distribution (using Student's t distribution with n-1 degree of freedom), then antilog transformations will be applied to the results of calculations, in order to provide geometric means (GMs) and their 95% CI.

GM is defined as follows:

$$GM = \left(\prod_{i=1}^n y_i \right)^{1/n} = 10^{\left(\frac{1}{n} \sum_{i=1}^n \log_{10}(y_i) \right)}$$

where (y_1, y_2, \dots, y_n) are the observed titers or other data where applicable for each subject. Rounding rules on descriptive statistics will follow the Sanofi Pasteur standard technical guideline ("Conventions for the Presentation of Descriptive Statistics").

5.1 Statistical Methods

5.1.1 Hypotheses and Statistical Methods for Primary Objective

For descriptive purposes, the statistics presented on Table 5.1 will be produced.

5.1.1.1 Hypotheses

No hypotheses will be tested.

5.1.1.2 Statistical Methods

All analyses will be descriptive. Safety will be assessed after each and any dose of CYD Dengue vaccine.

For the main parameters, 95% CIs of point estimates will be calculated using the normal approximation for quantitative data and the exact binomial distribution (Clopper-Pearson method) for single proportions.

The analysis of safety will address the number and percentage of subjects with injection site or systemic AEs until 28 days following each injection (solicited systemic reactions from D0 to D14, solicited injection site reactions from D0 and D7 and unsolicited AEs until D28, including AESIs and immediate unsolicited AEs, ie, occurring within 30 minutes after each vaccination).

Solicited reactions will be described according to their intensity and according to time of onset, number of days of occurrence, action taken, and according to whether they lead to trial discontinuation.

Unsolicited AEs will be described by Medical Dictionary for Regulatory Activities (MedDRA) SOC and preferred term definition according to their relationship, severity, time to onset, leading to study discontinuation and duration.

Serious and non-serious AESIs (in defined time windows according to the type of AESI) and SAEs (throughout the trial; including the 6-month follow-up) will be described by MedDRA SOC and preferred term, outcome, seriousness and relationship to vaccination.

The number and percentage of subjects with a hospitalized suspected dengue cases virologically-confirmed at any time throughout the trial after the injection will be described.

5.1.2 Hypotheses and Statistical Methods for Secondary Objectives

5.1.2.1 Hypotheses

No hypotheses will be tested.

5.1.2.2 Statistical Methods

For descriptive purposes, the statistics presented on Table 5.1 will be produced.

The proportion of subjects with a detected and quantified CYD dengue vaccinal viremia (ie, above the detection level) whatever the serotype (as assessed by YF RT-PCR) and for each of the four dengue serotypes (by serotype-specific CYD RT-PCR method) after the first CYD dengue vaccine injection will be presented at V02 and V03.

Number of subjects and percentages having a decrease in CD4 > 30% post-injection compared to pre-injection values and confirmed decrease in CD4 > 30% after each injection, not explained by non-adherence to ART and not explained by any other possible etiology, as well as an increase in HIV viral load post-injection and confirmed increase in HIV viral load (ie, plasma HIV-1 RNA < 50 copies/mL pre-injection and > 1000 copies/mL post-injection) for each injection, not explained by non-adherence to ART and not explained by any other possible etiology will be presented.

Analysis of dengue neutralizing antibody levels will be performed in each vaccine group before first injection (at baseline) and 28 days after each injection using:

- GMTs against each serotype with the parental dengue virus strains
- GM of individual titer ratio (GMTR) against each serotype with the parental dengue virus strains (post-Injection 1/pre-Injection 1, post-Injection 2/pre-Injection 1, and post-Injection 3/pre-Injection 1)
- Number and percentage of subjects ≥ 10 (1/dil) against each dengue serotype with the parental dengue virus strains at each available time point
- Number and percentage of subjects ≥ 10 (1/dil) against at least 1, 2, 3, or 4 dengue serotypes with the parental dengue virus strains at each available time point
- Number and percentage of subjects \geq various titer thresholds (1/dil) against each dengue serotype with parental dengue virus strains at each available time point
- Number and percentage of subjects \geq various titer thresholds (1/dil) for at least 1, 2, 3, or 4 serotypes with parental dengue virus strains at each available time point
- Distribution of titers against each of the 4 serotypes with parental dengue virus strains at each available time point and corresponding RCDCs
- Number and percentage of subjects immune and non-immune to YF, dengue, Zika and FV statuses at baseline

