3.1 Trial Design

This is a multicenter, observer-blind, randomized, placebo-controlled, Phase II study of the CYD dengue vaccine in 150 HIV-positive adults (18 to 50 years) in Brazil. Potential participants fulfilling all inclusion criteria, including a previous exposure to dengue according to a Rapid Diagnosis Test (RDT) or a dengue IgG enzyme-linked immunosorbent assay (ELISA), will be enrolled. Subjects will receive 3 injections of either CYD dengue vaccine or placebo at 0, 6, and 12 months. The enrollment of subjects will be carried out in two steps, including an early safety data review before the second step.

Subjects HIV-positive and previously exposed to dengue according to RDT or ELISA will be randomized in a 2:1 ratio into 1 of 2 groups:

- Group 1 (N=100): subjects will receive 3 doses of CYD dengue vaccine (live, attenuated, dengue serotype 1, 2, 3, 4 virus)
- Group 2 (N=50): subjects will receive 3 doses of placebo (NaCl 0.9%)

Each subject will have her / his dengue serostatus confirmed using both dengue PRNT and anti-NS1 IgG assay on the pre-injection blood sample. Subjects who are dengue-positive by RDT or ELISA at Screening Visit and dengue-negative by PRNT (sample collected before the first injection [at Visit 1] and assayed before second injection) will be considered as not previously exposed. Therefore, they will not receive any further injections and will be followed for safety until 6 months after the last dose. In addition, if they received the vaccine, provisions for timely access to medical care will be offered for 10 years after the last dose, according to IDMC prior recommendations.

All subjects are planned to be included in safety and immunogenicity analysis set. Blood samples will be taken at the Screening Visit (serology, hematology and biochemistry) if such a visit is required, and at several other time points throughout the study for baseline dengue, YF, and Zika serological status, CYD dengue vaccine immunogenicity, dengue vaccinal viremia post-Inj 1, and HIV status monitoring assessments, depending on the time points.

The duration of each subject's participation in the study will be approximately 18 months.

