4.4.2.2 Calculation Rules for the “at least X serotype(s)” Tables

The criteria below will be computed for each subject and visit as soon as at least one of the 4 dengue serotype results is different from missing or not-reportable (NR) (ie, coded no result in the serology database):

- Number and percentage of subjects with antibody titer ≥ 10 (1/dilution [dil]) against at least 1, 2, 3, or 4 serotypes with the parental dengue virus strains.
- Number and percentages of subjects with antibody titer \geq various titer thresholds (1/dil) against at least 1, 2, 3, or 4 serotypes with the parental dengue virus strains.

Titer(s) \geq to a threshold for at least X serotype(s) with parental dengue virus strains is computed as a Yes/No/Missing variable (note: in the case no titer is available the variable will be missing). If at least X among the 4 serotype titers meet the threshold considered then the variable is derived to “Yes”, otherwise if at least one titer is available and does not meet the threshold the variable is derived to “No”. For the percentage calculation, all the subjects with at least one titer available regardless of the serotype will be considered in the denominator.

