5.2.1 Full Analysis Set

The FAS is defined as the subjects who received either CYD dengue vaccine or placebo and had blood sample drawn and valid post-injection serology results (ie, a result different from “not-reportable” [“NR”] or missing, for at least one dengue serotype).

Subjects will be analyzed by the vaccine treatment group to which they were randomized.

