5.3.2 Immunogenicity

No imputation of missing values and no search for outliers will be performed. LLOQ and ULOQ management will be performed as described in Section 4.4.2.1.

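### Where PRNT-negative subjects stop injections, titers after injections 2 and 3 in the FAS (and in a per-vaccination PPAS) come from a different set than at baseline, and no matched table is planned

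*SAP*

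**What the plan says.** SAP 5.1.2.2 states: "Analysis of dengue neutralizing antibody levels will be performed in each vaccine group before first injection (at baseline) and 28 days after each injection". The outputs include GMTs, reverse cumulative distribution curves, and the number and percentage of subjects at or above 10, per serotype and "against at least 1, 2, 3, or 4 dengue serotypes with the parental dengue virus strains at each available time point". For the tables counting serotypes, SAP 4.4.2.2 says that "all the subjects with at least one titer available regardless of the serotype will be considered in the denominator". SAP 5.3.2 adds: "No imputation of missing values and no search for outliers will be performed".

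Of subjects who screen positive by RDT or ELISA but are dengue-negative by PRNT, SAP 3.1 says that "they will not receive any further injections and will be followed for safety until 6 months after the last dose". The deciding PRNT result comes from the "sample collected before the first injection [at Visit 1] and assayed before second injection". Protocol 5.1.1 carries the same rule, and it applies to both arms.

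On analysis sets, SAP 5.2.5 makes the PPAS the main immunogenicity set and uses the FAS to confirm it. The FAS (SAP 5.2.1) takes injected subjects who "had blood sample drawn and valid post-injection serology results" for at least one serotype. Both documents exclude from the PPAS anyone with an incomplete vaccination schedule. Protocol 12.2.3 adds that a separate per-protocol set is defined for each vaccination. SAP 5.2.2 does not repeat that sentence, but keeps the one that follows it, under which subjects stay in the corresponding population until they meet an exclusion. SAP 5.7 lists no change on this point.

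**The concern.** The V01 PRNT sample does two jobs. It is the baseline of the titer tables, and it decides who receives injections 2 and 3. V06 and V08 are timed from those injections. A PRNT-negative subject therefore has a V01 and a V04 titer and no planned titer afterwards, and is removed from the later rows because of a value on the outcome itself, at its floor.

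The secondary objective is to describe the humoral response at baseline and after each injection, so readers will compare rows across visits. In a set that contains these subjects at V01 and V04 but not at V06 and V08, part of the difference between rows can be a change in who is counted. In the placebo arm, such a step could be misread as natural boosting. No planned output separates the two: there is no common-cohort table, and the subgroup tables by baseline dengue status (SAP 5.1.4) classify subjects by anti-NS1 IgG (SAP 4.4.2.3), not by PRNT.

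**Working it through.** **Plan's own figure.** The only design probability stated is 95% for seeing an event of 3% incidence among 100 vaccinees: 1 - 0.97^100 = 0.952. It reproduces. The plan gives no figure for the PRNT-negative share or for titer levels.

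**Inputs from the documents.** The LLOQ is 10 (SAP 4.4.2.3). A titer below it counts as 0.5 x 10 = 5 in a GMT (SAP 4.4.2.1). Group sizes are 100 and 50 (SAP 5.5).

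**Assumptions.** PRNT-negative means below 10 to all four serotypes (the documents state no cut-off). A share q of the set is PRNT-negative. The others have GMT G. Nobody's titer changes, and every PRNT-positive subject stays at or above 10 to at least one serotype.

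**Which sets change composition**
1. FAS: one valid post-injection result is enough, so a V04 titer qualifies. These subjects are in the V01 and V04 rows and absent later.
2. PPAS defined per vaccination: they satisfy inclusion criterion 7 through the screening test, so they can be in the injection 1 set and then drop out. The composition changes in the same way.
3. PPAS as a single set: the incomplete schedule excludes them at every visit, so there is no change.

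**Size of the shift**
- GMT with these subjects: G^(1-q) x 5^q. GMT without them: G.
- Ratio: G / (G^(1-q) x 5^q) = (G/5)^q. For example, q = 5% and G = 100 give 20^0.05 = 1.16.
- Percentage at or above 10 to at least one serotype: from 100(1-q) to 100.
- Chance of at least one such subject among 50 placebo subjects: 1 - (1-q)^50.

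| q | GMT ratio, G = 100 | GMT ratio, G = 500 | At least 1 serotype ≥10 | Chance of any among 50 |
|---|---|---|---|---|
| 1% | 1.03 | 1.05 | 99% to 100% | 39% |
| 2% | 1.06 | 1.10 | 98% to 100% | 64% |
| 5% | 1.16 | 1.26 | 95% to 100% | 92% |
| 10% | 1.35 | 1.58 | 90% to 100% | 99.5% |

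For a row in which a proportion p of PRNT-positive subjects qualify, the percentage goes from p(1-q) to p. With p = 80% for all four serotypes and q = 10%, that is 72% to 80%.

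**Simulation check** (n = 50, G = 200, log10 SD 0.6, four correlated serotypes, no response). The mean GMT goes from 190 to 205 at q = 2%, from 171 to 205 at 5% and from 142 to 204 at 10%. At q = 0 it stays at 204.

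**Where the factor applies.** It applies to later rows against baseline in both arms, and against V04 in placebo. The step occurs once, between V04 and V06. In vaccinees, the V04-to-V06 step has the factor (G4/g4)^q, where G4 and g4 are the post-injection 1 GMTs of PRNT-positive and PRNT-negative subjects. The value of g4 is unknown because these subjects have had a vaccine dose.

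**After the fix.** With the same subjects at all visits and no response, the GMT ratio is 1.00 and the percentages do not move.

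**The case against.** The strongest reply is that the main analysis may be untouched. The PPAS leads, and SAP 5.2.2 read as one set excludes these subjects throughout. That stands, and it limits the point to the confirmatory FAS and to a per-vaccination PPAS. It does not dispose of the point, because the SAP wording supports either reading.

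Second, the effect needs q above zero. SAP 5.7 calls both screening tests very specific but gives no figure. At q = 1 to 2% the chance that 50 placebo subjects include none is 61% to 36%. With an assumed log10 SD of 0.6, the 95% interval of a GMT at n = 50 is about ×/÷ 1.48, so even the shift at q = 5% lies inside it. This stands as a limit on size. The shift is nonetheless always upward, and the protocol plans for such subjects.

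Third, sampling may not stop. The rule speaks of safety follow-up without saying that nothing else is collected. Protocol 5.2.7 opens by naming seronegative persons, and 5.2.7.2 continues immunogenicity assessments, as applicable, after a definitive contraindication. PRNT-negativity is not on that numbered list, so the documents leave this open.

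Fourth, safeguards exist. Each GMTR compares a subject with themselves, and SAP 4.4.2.1 sets the ratio to 1 when both titers are below the LLOQ. Same-visit comparisons between arms are not biased, since the rule uses a pre-injection titer in both arms. Both stand, but neither covers GMTs, percentages or distribution curves read across visits.

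**Conclusion.** The point holds in a limited form. In the FAS, and in a PPAS defined per vaccination, the planned tables let the removal of PRNT-negative subjects look like a rise from baseline (in placebo, also from V04). The size is the table above; it rests on assumed q and G and on the assumed meaning of PRNT-negative.

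A reader might infer more, and the documents do not support it:
- That titers will rise in the main analysis of both arms whatever happens. This depends on q and on how the PPAS is read.
- That seropositivity to at least one serotype reaches 100% by design. The PRNT cut-off and number of serotypes are not stated, and a PRNT-positive subject can later fall below 10.
- That vaccinees' V04-to-V06 step is inflated by (G/5)^q. Their response to injection 1 is unknown.
- That these subjects leave the trial. They stop injections and remain in safety follow-up.

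The analysis is secondary and descriptive, with no hypothesis at risk. The change is worth making because it is cheap and no planned output does the job.

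**What to change.** 1. In SAP 5.2.2, state whether the PPAS is one set or one per vaccination, and reconcile this with Protocol 12.2.3.
2. Reconcile SAP 3.1 and Protocol 5.1.1 with Protocol 5.2.7.2 on whether PRNT-negative subjects continue immunogenicity sampling.
3. In SAP 5.1.2.2, beside the available-case tables, show for each post-injection time point the baseline GMT and percentage at or above 10 (per serotype and by number of serotypes) for the same subjects who contribute at that time point.
4. Add one series of GMTs, percentages at or above 10 and distribution curves on subjects with valid titers at all four time points.
5. Base statements about change across injections on these rows and on the paired GMTRs.

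Items 3 to 5 need no new data. The cost is SAP wording, a few table columns, and a somewhat smaller common set, which also loses subjects missing a visit for unrelated reasons. That is why it goes beside the planned tables and does not replace them.

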5.1.3 Statistical Methods for Observational Objectives

5.1.3.1 Hypotheses

No hypotheses will be tested.

5.1.3.2 Statistical Methods

For descriptive purposes, the statistics presented on Table 5.1 will be produced for neutralizing Ab levels (measured by YF PRNT) against FV (dengue, YF and Zika) at baseline.

5.1.4 Complementary Outputs

Analyses of the immunogenicity and safety by baseline YF, dengue, Zika and FV statuses respectively will be provided in Appendix 15 of the clinical study report (CSR).

Immunogenicity analyses

- Summary of GMTs and GMTRs against each serotype with the parental dengue virus strains
- Number and percentage of subjects ≥ 10 (1/dil) against each dengue serotype with the parental dengue virus strains at each available time point
- Number and percentage of subjects ≥ 10 (1/dil) against at least 1, 2, 3, or 4 dengue serotypes with the parental dengue virus strains at each available time point

Safety analyses

- Safety overview
- Summary of solicited reactions and unsolicited AEs
- Solicited reactions and unsolicited AEs/ARs by maximum intensity
- Unsolicited AEs/ARs and Immediate AEs by MedDRA SOC and preferred terms
- Overview of SAEs

COVID-19

Impact of COVID-19 pandemic on study conduct and disposition of participants impacted by COVID-19 pandemic situation will be summarized in tables on all participants and listed in Appendix 16 of the CSR.

If more than 10% of randomized participants are impacted by COVID-19, and still evaluable for immunogenicity/safety timepoints, additional analyses in impacted/non-impacted participants will be done on main immunogenicity and safety endpoints.

